Protocol

**TITLE**: Dual benefits of Vaginal Estriol: improved urogenital health and re-myelination in relapsing remitting multiple sclerosis (RRMS)?

INVESTIGATORS:

- 1. [name]
- 2. [name]
- 3. [name]
- 4. [name]
- 5. [name]
- 6. [name], PhD

AIMS:

- 1. To evaluate the efficiency of vaginal estriol, as a treatment for urogenital symptoms in female patients with RRMS.
- 2. To evaluate the potential role of vaginal estriol in re-myelination in RRMS patients.

The goal of this pilot project is to determine the effectiveness of 1 mg transvaginal estriol, as an adjunctive therapy for female MS patients. Our goal is to recruit 20 patients from our MS clinic in the neurology department of Texas Tech University Health Sciences Center. This study has been planned in collaboration with reproductive endocrinology, endocrinology, gynecology and basic science. The 1mg transvaginal dose was chosen after careful search of the literature and consultation with our collaborators.

OBJECTIVES:

- Aim 1: Define if transvaginal estriol improves urogenital symptoms (urgency, frequency, intermittent incontinence), in female patients with Relapsing Remitting MS (RRMS). Bladder control scale, will be given at baseline, 3, 6, and 9 months after starting transvaginal estriol. Quality of life questionnaire will be given at baseline and at 9 months after starting vaginal estriol.
- Aim 2: Assess for evidence of re-myelination associated to the use of transvaginal estriol in woman with MS. Objective measurements for re-myelination will be quantified with brain MRI 3T, Optical coherence tomography (OCT)-and Visual evoked potentials (VEP).

INTRODUCTION / BACKGROUND / SIGNIFICANCE:

More than 2.3 million persons suffer from MS worldwide. Demyelination and axonal loss are the main pathological process in MS. Unfortunately remyelination occurs an incomplete fashion (Mallik, Samson, Wheeler-Kingshott, & Miller, 2014). Experimental models of MS have shown that preservation of myelin and remyelination of axons can increase neuronal survival. Until now, treatment for MS may decrease the relapse rate and progression, without any significant effect on remyelination.

Urinary issues in MS

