• Optical coherence tomography (OCT) (noninvasive scan of the retinal layer which provides morphology imagery of the ganglion cell layer which is frequently affected in MS) (Noninvasive test, duration of about 5 to 10 min to perform, patient has to stay still and focus on a small light while we take a picture of the retina layer with the device.)

Data Sheet: A spreadsheet is attached. We will be gathering demographic data, MRI information, EDSS score, and electrophysiologic information, for details please see the spreadsheet attached.

Outcome variables:

1- Urogenital symptoms such as frequency, incontinence, frequent urinary tract infections, and BLCS questionnaire scores.

2- Remyelination (measured by brain MRI 3 DTI, other measurements include presence of T2 lesions, Flair lesions, DWI, T1 black hole, and DTI; Optical coherence tomography (OCT); and visual evoked potentials (VEP).

3- Quality of life, assessed using MSQOL-54 questionnaire.

Analysis:

Patient characteristics will be summarized using frequency (percentage) for categorical variables, and mean (SD) or median (interquartile range) for numerical variables as appropriate. Changes in blood work variables during the course of the study will be assessed using one-way repeated-measures analysis of variance (ANOVA). Compliance assessments will be used as covariate to adjust the differences if necessary, using an analysis of covariance model (ANCOVA). Urinary symptoms, and quality of life data will be analyzed using mixed-effects linear or logistic regression models for continuous or binary outcomes respectively. These models will account for the effect of estriol over time, compliance with treatment, and relevant patient characteristics.

Justification for Sample size:

This is a pilot study. We are planning to include 20 patients. Each patient will be their own control in a single-group repeated measures design. Assuming a significance level $\alpha = 0.05$, and power 1- $\beta = 0.80$, a

TEXAS TECH UNIVERSITY HEALTH SCIENCES CENTER IRB NUMBER: L19-020 IRB APPROVAL DATE: 12/13/2019

sensitivity power analysis determined that a moderate effect size (d=0.53 to d=0.66) would be required to detect statistically significant changes in the main outcome.

Risks

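### Is the lower end of the detectable effect range, d = 0.53, out of reach with 20 patients?

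*Combined protocol and SAP*

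**What the plan says.** Justification for Sample size calls the trial a pilot and fixes the number of patients first: "We are planning to include 20 patients". It then describes the design: "Each patient will be their own control in a single-group repeated measures design". With alpha 0.05 and power 0.80, it reports that a "sensitivity power analysis determined that a moderate effect size (d=0.53 to d=0.66) would be required to detect statistically significant changes in the main outcome". The main outcome, test, sidedness, number of visits, within-patient correlation and definition of d are not given, nor is the reason for a range.

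The section Analysis supplies the planned model: "Urinary symptoms, and quality of life data will be analyzed using mixed-effects linear or logistic regression models for continuous or binary outcomes respectively". Objectives, Aim 1 supplies the visit pattern for the bladder scale: "Bladder control scale, will be given at baseline, 3, 6, and 9 months after starting transvaginal estriol". The same aim and the Schedule of events place the MSQOL-54 at two visits only, baseline and month 9.

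**The concern.** With each patient as her own control, the natural first check is a paired t-test on 20 within-patient changes. It returns the upper end of the range and misses the lower end clearly, and a one-sided test does not close the gap. A reader who took 0.53 as a baseline-to-follow-up change in units of the SD of the change would credit the trial with 80% power where a paired test has about 61%, and might then read too much into a null result. This sentence is also the only quantitative support offered for 20 patients, so an unsupported figure in it deserves checking.

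**Working it through.** **Inputs from the protocol:** n = 20, alpha 0.05, power 0.80; four bladder-scale visits and two MSQOL-54 visits. **Assumed, because not stated:** two-sided testing unless noted, equal variances and equal correlations ρ between visits, no dropout.

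**1. Paired comparison, two visits, d in SD-of-change units.** Power is P(T > t-crit), where T is noncentral t with 19 df and noncentrality d√20.
- Two-sided (t-crit 2.093): 80% power at d = 0.660. At d = 0.66 the noncentrality is 0.66 × 4.472 = 2.95 and power is 79.9%. The upper end reproduces.
- Two-sided at d = 0.53: noncentrality 0.53 × 4.472 = 2.37, power 61.4%.
- One-sided: detectable d = 0.577; power at 0.53 is 73.9%.

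No paired test with 20 patients gives 0.53.

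**2. Repeated-measures F test, m visits.** Degrees of freedom are m − 1 and 19(m − 1), λ = f² × 20 × m / (1 − ρ), sphericity holds, and d = 2f.

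| Visits | ρ (assumed) | Detectable d = 2f | Power at d = 0.53 |
|---|---|---|---|
| 2 | 0.5 | 0.660 | 61.4% |
| 4 | 0.3 | 0.639 | 62.2% |
| 4 | 0.5 | 0.540 | 78.3% |
| 4 | 0.52 | 0.529 | 80.1% |
| 4 | 0.7 | 0.419 | 95.4% |

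For the four-visit row at ρ = 0.5, d = 0.53 means f = 0.265 and λ = 0.265² × 80 / 0.5 = 11.24, just short of the 11.68 needed for 80% power. A single assumption, ρ = 0.5, therefore gives 0.66 for an outcome measured twice and 0.54 for one measured four times. These are the two visit counts in the protocol.

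**3. Four-visit contrasts, d in SD of a single-visit change.** A single-visit change has variance 2σ²(1 − ρ).
- Mean of three follow-ups minus baseline: variance σ²[1 + (1 + 2ρ)/3 − 2ρ] = (4/3)σ²(1 − ρ), so the SD ratio is √(2/3), whatever ρ is. If the full effect is present from month 3, detectable d is 0.660 × 0.816 = 0.539 with 19 df, or 0.520 with 57 df. Power at 0.53 is 78.6% or 81.4%.
- Linear trend scaled to month 9: weights −0.9, −0.3, 0.3, 0.9 have sum of squares 1.8, so the SD ratio is √(1.8/2) = √0.9. If the effect builds linearly, detectable d is 0.627 (19 df) or 0.605 (57 df), and power at 0.53 is 65.9% or 69.0%.

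The four-visit contrasts thus run from 0.52 to 0.63, according to the shape of the response.

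**The case for a change.** The strongest case for acting is that none of these routes to 0.53 is stated and that the figure is sensitive to them. Correlations of 0.3 to 0.7 move the four-visit result from 0.64 to 0.42, and only about 0.51 to 0.53 rounds to 0.53. The convention d = 2f also equals the largest difference between visits only when two visits sit at one level and two at another. At ρ = 0.5 (f = 0.270), where the raw SD equals the SD of a change, the same F test needs a baseline-to-follow-up change of 0.270/0.433 = 0.62 if the full effect is present at every follow-up, and 0.270/0.373 = 0.72 if it builds linearly. Finally, the protocol speaks of one main outcome, so a range spanning two visit counts leaves the reader unsure which end applies.

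All of this stands as a criticism of the reporting. It does not show that 0.53 was miscalculated. The follow-up-mean contrast brackets 0.53 without using the 2f convention or any particular correlation, though it does need an early, sustained effect. The 0.66 end rests on unstated choices too: two-sided testing, and either a paired test or ρ = 0.5.

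Replacing the range by the paired figure alone would be no clear gain. It would describe a two-visit test that the protocol does not propose, and it is conservative for a four-visit mixed model when correlation is moderate or high. Adding detectable effects for 18 or 16 completers (0.70 and 0.75) would bring in dropout levels that the protocol does not contain.

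**Conclusion.** The concern does not hold as an arithmetic error. With 20 patients, 0.66 is the two-sided two-visit paired value. The lower figure is recovered to within about 0.01 by four-visit analyses that fit the stated design: 0.54 at correlation 0.5, 0.53 at 0.52, and 0.52 to 0.54 for baseline against the mean of follow-ups with the full effect from month 3. Correlation and response shape are assumptions, and the documents do not show which calculation was run, so this is a plausible account of the range and not a confirmed one.

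The gap left is incomplete description of a sensitivity calculation. Its consequence is small: the 20 patients were chosen first, the less favourable 0.66 stands in the same parenthesis, and no analysis or decision rule uses d. An analyst interpreting a null result would rely on the confidence interval from the fitted mixed model and not on this range. No change to the plan is needed.

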- 2. Baseline urogenital status will be evaluated by
 - Bladder Control Scale (BLCS) questionnaire
- 3. Multiple Sclerosis Quality of Life-54 (l-54) questionnaire will be completed
- 4. Baseline Visual Evoked Potential (VEP) within 4 weeks of Initial Visit
- 5. Optical Coherence Tomography (OCT) (occurs at the Ophthalmology clinic) within 4 weeks of Initial Visit
- 3 Tesla brain MRI will be performed as well. (within 3 months of initial visit)
- Dispense vaginal estriol cream once all baselines are complete

The primary investigators will instruct how to correctly use vaginal cream. Patients will be instructed to draw 1 mg of estriol vaginal cream with the applicator and apply intravaginally. They will be instructed to lay on their back for 30 min after vaginal cream application once a day for the duration of the study. The applicator is reusable, cleaning technique will also be given to the patient during their visit and reinforced during follow up. The applicator will be washed with regular soap and water and let air dry.

Patients will be instructed not to start applying vaginal cream until baseline lab work and imaging has been performed.

Three-month visit (90 days +/- 10 days):

- BLCS questionnaire will be completed
- Blood will be collected for serum estriol, FSH and LH level. (about 20 ml of blood)
- VEP and OCT will be also performed. ± 3 weeks of 3 month Visit
- Dispense vaginal estriol cream

Six-month visit (180 days +/- 10 days):

- BLCS questionnaire will be completed
- Blood will be collected for serum estriol, FSH and LH level. (about 20 ml of blood)
- VEP and OCT will be also performed. ±-3 weeks of 6 month Visit
- Dispense vaginal estriol cream

Nine-month visit (270 days +/- 10 days-FINAL VISIT):

- BLCS and MSQOL-54 questionnaires will be completed
- Blood will be collected f serum estriol, FSH and LH level. (about 20 ml of blood)
- 3 Tesla brain MRI will be repeated. \pm 3 months of 9 month Visit

During each visit patients will be questioned for adverse events, patients will also have a number to call in case of questions, concerns or adverse events.

Due to the nature of RRMS there might be acute exacerbations in which the patient will be treated with IV methylprednisolone 1gm a day x 3 to 5 days, this is the standard of care for MS exacerbations.

Schedule of events

Procedures	Screening visit	3 month visit	6 month visit	9 month visit FINAL VISIT
Date				
ICF	Х			
1&E	Х			
Blood work	x	x	x	x
BLCS	x	x	x	x
questionnaire				

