To ensure compliance of the study protocol, GCP guidelines, and TTUHSC Human Research Protection Program research policies and procedures during the conduct of the study, a monitor in the Clinical Research Institute will conduct the monitoring of the study. The first monitoring visit will be conducted within two weeks after the first subject has been enrolled into the study. The succeeding monitoring visits will be scheduled periodically, but no less than every 2 months when there is an active study participant, at a mutually agreed timeframe by the PI and study monitor. All data collected will be 100% source document verified. The study monitor may inspect and audit all study documents, i.e. data collection forms, questionnaires, drug accountability, and medical records within the applicable confidentiality regulations.

Reimbursement:

No reimbursement for the participants

Funding: Laura W. Bush Institute for Women's Health and University Medical Center Women's Health Research Scholar Fund and the TTUHSC Department of Neurology.

Acknowledgements:

The investigators would like to express our sincere gratitude to the Clinical Research Institute and Department of Neurology at TTUHSC, Lubbock, Texas for assistance.

References:

- Cody, J. D., Jacobs, M. L., Richardson, K., Moehrer, B., & Hextall, A. (2012). Oestrogen therapy for urinary incontinence in post-menopausal women. In *Cochrane Database of Systematic Reviews*. https://doi.org/10.1002/14651858.CD001405.pub3
- Harlow, D. E., Honce, J. M., & Miravalle, A. A. (2015). Remyelination therapy in multiple sclerosis. *Frontiers in Neurology*, 6(DEC), 1–13. https://doi.org/10.3389/fneur.2015.00257
- Moore, K. H. (2001). The costs of urinary incontinence. *Medical Journal of Australia*, 174(9), 436–437. https://doi.org/10.2165/00019053-199406020-00009

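### The stated detectable effect (d=0.53 to 0.66 at 80% power) is computed for 20 analysed women, the same number the plan aims to recruit, so it holds only if no one is lost

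*Combined protocol and SAP*

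**What the plan says.** The statement of the project's goal, under AIMS, reads: "Our goal is to recruit 20 patients from our MS clinic". Justification for Sample size reads: "We are planning to include 20 patients". It describes the design as follows: "Each patient will be their own control in a single-group repeated measures design". With alpha 0.05 and power 0.80, it reports that a "sensitivity power analysis determined that a moderate effect size (d=0.53 to d=0.66) would be required to detect statistically significant changes in the main outcome". It does not name the main outcome, the test, or whether the test is one- or two-sided, and it does not say whether the 20 are women consented, treated or analysed.

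No section gives a dropout rate, an inflation of the recruitment target, a replacement rule, an analysis set or a missing-data rule.

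Under Study visits, eligibility is confirmed after consent, and the last baseline step is: "Dispense vaginal estriol cream once all baselines are complete". VEP and OCT may fall up to 4 weeks from the initial visit, and the MRI up to 3 months. BLCS is collected at baseline and at 3, 6 and 9 months. MSQOL-54 is collected only at baseline and month 9. The Analysis section assigns urinary symptoms and quality of life to mixed-effects models.

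**The concern.** If the number recruited equals the number in the power calculation, every loss makes the detectable effect larger than stated. There are two routes to loss. A woman may consent and then fail the eligibility check or not complete the baseline tests, in which case she never receives cream and has no on-treatment data. Or she may start daily cream and stop attending before month 9. On participant payment the protocol says: "No reimbursement for the participants".

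The range is the only quantitative support given for 20. A reader judging a non-significant result will look to it to see what the trial could have found, and will overestimate that if fewer than 20 women are analysed.

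**Working it through.** **Inputs.** From Justification for Sample size: n = 20, alpha = 0.05, power = 0.80, within-patient design, stated range d = 0.53 to 0.66. From the visit schedule: four BLCS time points, two MSQOL-54 time points. Loss rates of 10, 20 and 30% (18, 16 and 14 women left of 20) are my assumption.

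**Reproducing the 0.66 end.** For a two-sided paired t-test, power = P(|T| > t(0.975, n−1)), where T is noncentral t with n−1 degrees of freedom and noncentrality d√n. With n = 20 the critical value is 2.093 and the noncentrality at d = 0.66 is 0.66 × √20 = 2.952. Power is 0.799, and solving for exactly 0.80 gives d = 0.660. A one-sided test gives 0.577 and the two-sided normal approximation 0.626, so the two-sided t-test on 20 complete pairs is the match.

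**The 0.53 end.** More than one method reproduces it with n = 20. A two-sided Wilcoxon signed-rank test with a Laplace parent (relative efficiency 1.5, effective n = 30) gives 0.529. A paired t-test with d expressed in raw standard deviations and a correlation of about 0.68 gives 0.660 × √(2 × 0.32) = 0.528. The protocol does not say which was used, but both use all 20 women.

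**Where a lost woman contributes no change from baseline** (never started cream, or MSQOL-54 with no month-9 value). The 0.66 end is re-solved with the same formula. The 0.53 end is scaled by √(20/n), because its test is unknown; this ignores the loss of degrees of freedom, so it is slightly low.

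| Women analysed | Assumed loss | 0.66 end becomes | Power at d = 0.66 | 0.53 × √(20/n) |
|---|---|---|---|---|
| 20 | 0% | 0.66 | 0.80 | 0.53 |
| 18 | 10% | 0.70 | 0.75 | 0.56 |
| 16 | 20% | 0.75 | 0.69 | 0.59 |
| 14 | 30% | 0.81 | 0.63 | 0.63 |

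A single loss (n = 19) gives 0.68, with power 0.78 at d = 0.66.

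**BLCS, where early leavers still contribute.** In a mixed model, a woman who leaves after month 3 or month 6 keeps her earlier scores in the analysis. I assumed compound symmetry with correlation 0.5 to 0.7 over the four visits, all 20 women starting, and leavers split evenly between after month 3 and after month 6. Generalised least squares gives the variance of the month-9 minus baseline contrast by summing the inverse covariance blocks for the visits each woman has. The detectable effect is 0.66 × √(variance with losses / variance with 20 complete).

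| Completers | Variance ratio (correlation 0.5 to 0.7) | Month-9 change | Average post-baseline change |
|---|---|---|---|
| 18 | 1.072 to 1.075 | 0.68 | 0.67 |
| 16 | 1.161 to 1.168 | 0.71 | 0.68 |
| 14 | 1.275 to 1.287 | 0.75 | 0.68 to 0.69 |

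This scaling also leaves out the change in degrees of freedom. With complete loss at n = 14, scaling alone would give 0.66 × √(20/14) = 0.79 rather than 0.81, so a small part of the gap between the two tables comes from the method.

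**The case against.** The strongest reply is that there is no error: with 20 women analysed the figure is right, and any shortfall depends on losses the documents do not quantify. That stands. The defect is an unstated assumption, not wrong arithmetic, and a reader who infers that the design cannot deliver its figure goes beyond the text.

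A reader might also infer that women who never start cream are counted among the 20. No section says so. The protocol uses both recruit and include without defining either, and under Initial visit it still treats women as potential participants while eligibility is being checked. Nor is loss before treatment certain. Under Methods, Subjects, women are screened before being invited. The Inclusion criteria require that they are already being prescribed vaginal estriol. Enrolment is tied to an MRI done as standard care, and participants are to be contacted routinely. This makes non-starters less likely but does not rule them out, and the plan does not say what happens to their places.

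It would also be tempting to apply 0.70 to 0.81 to every outcome. For BLCS, which belongs to Aim 1 and the first listed outcome, the planned mixed model keeps early leavers' scores and the effect is smaller. The power sentence refers only to an unnamed main outcome and is not stated to cover MSQOL-54 or MRI.

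Finally, this is a pilot with a sensitivity analysis at a fixed n. Nothing in the plan proposes to read a null result as excluding d = 0.66, and a non-significant result at 80% power would not exclude it in any case. That limits the consequence but does not remove the case for stating the assumption.

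**Conclusion.** The point holds as a conditional one. The range of 0.53 to 0.66 is correct for 20 analysed women and makes no allowance for loss, while the recruitment goal is the same 20 and no replacement rule is given.

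The size depends on where the losses fall. At an assumed 10% it is small on any reading: the 0.66 end moves to 0.68 for BLCS at month 9, or to 0.70 where lost women contribute nothing. At an assumed 30% it reaches about 0.75 and 0.81 respectively. The 0.53 end can be adjusted only by scaling until its test is named. All of this rests on assumed loss rates, and the BLCS figures also rest on the assumed correlation structure and timing of departures. Severity is minor.

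**What to change.** In Justification for Sample size, restate the detectable effect for the number of women expected to be analysed. Name the main outcome and the test behind each end of the range, keep both ends, and label the loss rate as an assumption. If no local rate is available, a short range such as 10 to 30% will do. If the main outcome is BLCS under the mixed model, use figures for that analysis rather than for complete pairs.

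State also that the 20 places are counted at first dispensing of cream, so that women who consent but never start do not use them up. This deals only with losses before treatment; later departures are covered by the restated figure.

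The cost is a couple of sentences and a slightly less favourable stated figure. A few more women may need to be consented, but no more than 20 would be treated.

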Urinary dysfunction includes frequency, incontinence, frequent infections, occurs in about 80-90% of MS patients. It causes a major disruption in daily life, imposing economic burdens for patients and their families. Direct costs and indirect costs as psychological distress, loss of productivity are a significant burden for the patient, and increase the risk of unemployment.(Moore, 2001) Besides interfering with quality of life, urinary dysfunctions leads commonly to urinary tract infections which can have a direct impact on MS, worsening neurologic symptoms, and increasing in the number of relapses, which may lead to disability.

Estriol for urogenital health

Urinary dysfunction is frequently treated with antimuscarinic agents; side effects from these drugs (dry mouth, blurred vision, constipation and difficulty with micturition) make compliance an issue (David et.al). Transvaginal estriol decreases urinary symptoms and prevents urinary tract infections.(Rahn et al., 2014) There is less risk of endometrial hyperplasia and endometrial cancer with estriol treatment compared with estradiol treatment (Cody, Jacobs, Richardson, Moehrer, & Hextall, 2012). Furthermore, vaginal delivery offers regional benefits to the lower urogenital tract, it is well absorbed and it is not associated with entero-hepatic recirculation as oral estriol, as some of the adverse effects of oral estrogens are to produce an increase in thromboembolic events. (Rahn et al., 2014)

Estriol in MS, role in remyelination

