- 1. Female patients with RRMS between the ages of 35 to 65.
 - A) Being prescribed vaginal estriol to treat their urogenital symptoms.
 - B) Patients that had underwent menopause or surgical hysterectomy.
- 2. Patients will continue their disease modifying agent for MS during the trial.

Exclusion criteria:

- 1. Patients with personal history of breast cancer, uterine or ovarian cancer.
- 2. Patients with history of fibrocystic breast disease, heart attack or stroke.
- 3. Patients with history of thromboembolism.
- 4. Patients with progressive multiple sclerosis
- 5. Patients who are unable to undergo an MRI
- 6. Males
- 7. Patient is already on vaginal or oral or transdermal estrogens
- 8. Pregnant or breast-feeding patients
- 9. Patient taking sex hormones eg testosterone for libido
- 10. Patients taking DHEA or OTC related products that could influence the hormonal milieu.
- 11. Patient with prolapse uterus or conditions that would impact on transvaginal absorption of estriol

Enrollment in the study will be timed to their follow up brain MRI which will be performed as standard of care. Patients that have no baseline MRI or are unable to undergo MRI will be excluded from the study.

Site of study: The TTUHSC department of Neurology, MS clinic, Lubbock, TX; The TTUHSC Department of Ophthalmology and Visual Sciences, Lubbock, TX

Design:

This is a single-group prospective repeated-measures pilot trial. Duration is 12 months

Intervention:

Estriol vaginal cream will be formulated by Twin Oaks Pharmacy's compounding pharmacy, Regional Pharmacy, by the same compound specialist. 30 mg estriol powder will be mixed with 5 mL of propylene glycol and 22 g of vaginal base cream. The product can be stored at room temperature and has a shelf life of up to 4 months. It comes with an applicator.

The 1 mg dosing was chosen due to evidence in previous trials, and a systematic review of randomized trials comparing vaginal estrogens. It was concluded that the 1mg vaginal estroid, was superior to lower doses for the treatment of urogenital symptoms. (Rahn et al., 2014).

Study visits/Roles of subjects:

Initial visit:

After the informed consent has been obtained and all questions have been addressed Potential participants will be screened to ensure they are eligible for the clinical trial. Once eligibility has

been verified

- 1. Blood will be collected for baseline laboratory studies serum estriol, FSH and LH level. (about 20 ml of blood)

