Studies suggest that when the lower-potency estrogen, estriol, is administered transvaginal, it does not increase the risk of hormone-dependent cancers of the breast or endometrium (uterine lining) Therefore the risk of breast and endometrial cancer is not increased with vaginal estriol. (Voojis et.al) Another safety concern of estrogens is the risk of thromboembolism. There is a paucity of prospective studies specifically looking at estriol and thromboembolism. Studies have shown that transdermal and transvaginal estrogen have a lower rate of thromboembolism. (Scarabin, Oger, & Plu-Bureau, 2003). Risks associated with venipuncture for blood draws include: discomfort, pain, bleeding, bruising, infection where the needle enters the skin; feeling lightheaded or fainting at the site of the needle or blood. No physical risk with VEP or OCT, these are noninvasive procedures.

Using the applicator or cream may cause vaginal discomfort or infection. Patients will be asked during their visits about vaginal discomfort or vaginal infections. Patients will also be encouraged to call if they are experiencing these. If the patient does experience these symptoms they may be referred to their PCP or Gynecologist for appropriate management.

Benefits:

Patients may experience improvement of her urogenital symptoms as well as improvement in their MS symptoms. Patient may have improved sexual function. Subjects could share satisfaction from potential benefits to other MS patients. May help revolutionize treatment of MS along with urogenital benefits at low cost

Confidentiality:

Patient's information will be de-identified and identifier information will be kept in a safe place. Electronic files will be locked by password which will be known by the principal investigator. Study documents will be kept at least 3 years then destroyed.

Study is registered at clinicaltrials.gov

Monitoring

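### Vaginal bleeding is not among the symptoms asked about by name, and no baseline bleeding status is specified, although women with a uterus may use daily estriol

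*Combined protocol and SAP*

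**What the plan says.** The Risks section names two local effects of the applicator or cream and provides that "Patients will be asked during their visits about vaginal discomfort or vaginal infections". Under Study visits there is a broader provision: "During each visit patients will be questioned for adverse events". Patients also get a number to call.

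Inclusion criterion 1B reads "Patients that had underwent menopause or surgical hysterectomy". Either condition is enough, so a menopausal woman with a uterus is eligible. Exclusion 11, which concerns uterine prolapse, also presupposes that some candidates have a uterus. The cream is applied once daily throughout, and the final visit is at day 270.

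The protocol raises endometrial effects itself. The section on estriol for urogenital health states "There is less risk of endometrial hyperplasia and endometrial cancer with estriol treatment compared with estradiol treatment". The Risks section goes further and concludes that vaginal estriol does not raise breast or endometrial cancer risk. The section on the benefit of vaginal estriol says the same of cancer in general. The Hypothesis describes the treatment as safe.

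**The concern.** The two symptoms asked about by name follow from the cream and applicator. They do not follow from the estrogenic risk that the same section has just discussed. A symptom that could bear on that risk has no named question, no recorded answer before treatment and no defined group in which to count it.

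This matters because the trial is a single group with each woman as her own control. If bleeding is reported at month 3 and no pre-treatment answer exists, whether it is new has to be reconstructed afterwards. A general question also depends on the woman thinking the symptom worth mentioning. The trial could then end with few or no bleeding reports and no way to tell whether that reflects the treatment or the questioning. The word safe in the hypothesis would rest on that.

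**Working it through.** **The plan's own figure.** The only precision statement concerns efficacy: "sensitivity power analysis determined that a moderate effect size (d=0.53 to d=0.66) would be required to detect statistically significant changes in the main outcome". A two-sided paired t test with n = 20 needs d = 0.660 for 80% power, which matches the upper end. A four-visit repeated-measures ANOVA gives d = 0.540 if the within-subject correlation is taken as 0.5, a value the plan does not state. Power at d = 0.53 is then 78.3%, so the lower end reproduces approximately. The plan states no safety sample size, event rate or precision.

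**Where bleeding could appear.**
- Eligibility: cancer history and uterine prolapse are listed; bleeding is not.
- Initial visit and Schedule of events: no bleeding item, and the schedule has no adverse-event row.
- Outcome variables and Analysis: no adverse-event outcome or summary.
- Risks: the only bleeding mentioned is at the venipuncture site.
- Data Sheet: the contents named are demographic, MRI, EDSS and electrophysiologic data. The spreadsheet itself is not in the documents.

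**Inputs.** N = 20 comes from the plan ("We are planning to include 20 patients"). The rest are assumptions:
- Share with hysterectomy 25% to 60%, leaving 15 to 8 women with a uterus (20 × 0.75 = 15; 20 × 0.40 = 8).
- True proportion with bleeding 2% to 10%.
- Capture of 100% for a named question, and 50% or 25% for a general one.

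**Chance of recording at least one woman with bleeding:** 1 − (1 − rate × capture)^n.

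| Women with a uterus | Rate | Capture 100% | 50% | 25% |
|---|---|---|---|---|
| 20 | 5% | 64% | 40% | 22% |
| 15 | 5% | 54% | 32% | 17% |
| 10 | 2% | 18% | 10% | 5% |
| 10 | 5% | 40% | 22% | 12% |
| 10 | 10% | 65% | 40% | 22% |

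For example, 1 − 0.95^10 = 40% and 1 − 0.975^10 = 22%.

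**Effect of the denominator.** With zero events, the one-sided 95% upper bound is 1 − 0.05^(1/n). It is 13.9% for n = 20, 18.1% for 15, 25.9% for 10 and 31.2% for 8. One event is 1/20 = 5% of all women, but 1/15 = 6.7% to 1/8 = 12.5% of those with a uterus.

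These bounds assume full capture. At 50% capture, zero recorded events in 10 women bounds the true rate only at 25.9% / 0.5 = 51.8%.

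**The case against.** The strongest reply is that a route already exists. Adverse events are asked about at every visit, and a phone line covers the time between. The sentence in Risks deals with local effects of the cream and is not offered as a complete list. That stands: bleeding could be recorded under the plan. What is missing is structured questioning with a baseline, not any means of capture.

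The data sheet is not visible and may hold a bleeding or uterine-status field. That also stands, so the point is limited to the visible text. Eligibility screening does not fill the gap, because a woman who qualifies by menopause may or may not have had a hysterectomy.

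A reader might infer that the protocol concedes a residual endometrial risk. It does not: the background sentence compares estriol with estradiol, and two other sections assert no increase. A reader might also infer that the trial will report a diluted rate over all 20 women. No adverse-event rate of any kind is planned, so the denominator figures show what pooling would do, not what the plan says.

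Nor is it right that later bleeding could never be placed in time, since onset can be asked when it is reported. Even a baseline answer would not establish causation without a control group.

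Finally, the documents do not say that bleeding marks an endometrial effect or that a named question captures more than a general one. Both are assumptions here, and the second is why a capture range is shown.

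**Conclusion.** The point holds as a gap in ascertainment. Women with a uterus can receive daily estriol in a trial whose hypothesis calls it safe, and the visible plan neither asks about vaginal bleeding by name nor specifies a bleeding status before treatment.

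The size is illustrative. With 10 women with a uterus, halving capture lowers the chance of recording any case from 18% to 10% at an assumed 2% rate, and from 65% to 40% at 10%. No aim, listed outcome or planned analysis depends on this, so it is a cheap improvement and not a flaw in the trial's main conclusions. With at most 20 women, even full capture leaves wide bounds, and endometrial safety would not be established.

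The two statements on endometrial risk should also be reconciled. One is relative to estradiol and covers hyperplasia as well as cancer. The other moves from what studies suggest to an unqualified conclusion about cancer only. The gap in questioning remains however that is settled.

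**What to change.** - In Risks and in the Schedule of events, add vaginal bleeding (yes/no, with dates) to the symptoms asked about by name at the initial visit, before the first application, and at months 3, 6 and 9.
- Record at baseline whether the woman has a uterus, unless the attached data sheet already does so.
- In Analysis, report bleeding separately for women with and without a uterus, each with its own denominator. Reporting only the former would lose any bleeding from the cream or applicator in women after hysterectomy.
- State the comparator and the outcome in each sentence on endometrial risk, so that the background and Risks sections agree.

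The cost is one question at four existing visits and one baseline field, with no added procedure, visit or staff. The downside is that more minor events will be recorded. How any reported bleeding is handled clinically is for the investigators to set.
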